2. STUDY OBJECTIVES

2.1 Primary objective

1. Assessment of longitudinal changes in allele frequency of ESR1 mutation in plasma in patients treated with Fulvestrant plus palbociclib compared to tamoxifen plus palbociclib
2. Assessment of genomic alterations (using MammaSeq) associated with wildtype or mutant ESR1
3. Assessment of the functionality of ESR1 in tumor biopsies collected prior to and following treatment with fulvestrant plus palbociclib, or tamoxifen plus palbociclib, as assessed by RNAseq
4. Safety and toxicity assessment

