- Complete Response (CR): Disappearance of all non-target lesions and normalisation of tumor marker level. All lymph nodes must be non-pathological in size (<10mm short axis).
- Non-CR/Non-PD: Persistence of one or more non-target lesion(s) and/or maintenance of tumor marker level above the normal limits.
- Progressive Disease (PD): Unequivocal progression of existing non-target lesions. (Note: the appearance of one or more new lesions is also considered progression).

Evaluation of Best Overall Response

The best overall response is the best response recorded from the start of the treatment until disease progression/recurrence (taking as reference for progressive disease the smallest measurements recorded since the treatment started). The patient’s best overall response assignment will depend on the findings of both target and non-target disease and will also take into consideration the appearance of new lesions.

TABLE 2. Time to response definition

Target Lesions	Non-Target Lesions	New Lesions	Overall Response
-----------------------	---------------------------	--------------------	-------------------------

CR	CR	No	CR
CR	Non CR/Non PD	No	PR
CR	Not evaluated	No	PR
PR	Non PD or not all evaluated	No	PR
SD	Non PD or not all evaluated	No	SD
Not all evaluated	Non PD	No	NE
PD	Any	Yes or no	PD
Any	PD	Yes or no	PD
Any	Any	Yes	PD

CR= complete response, PR= partial response, PD= progressive disease, SD= stable disease, NE= not evaluable.

Note: Patients with a global deterioration of health status requiring discontinuation of treatment without objective evidence of disease progression at that time should be reported as “*symptomatic deterioration*”. Every effort should be made to document the objective progression even after discontinuation of treatment.

Progression Free Survival

PFS is defined as the duration of time from time of randomization to time of progression or death, whichever occurs first. PFS for a subject without an event will be censored on the date of last tumor assessment. If an interval of 6 months passes without a tumor assessment, PFS will be censored at the time of the earlier tumor assessment, even if an event (progressive disease or death) is later observed.

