When collecting AEs, the recording of diagnoses is preferred (when possible) to recording a list of signs and symptoms. However, if a diagnosis is known and there are other signs or symptoms that are not generally part of the diagnosis, the diagnosis and each sign or symptom will be recorded separately.

Adverse Events based on examinations and tests

If deterioration in a laboratory value/vital sign is associated with clinical signs and symptoms, the sign or symptom will be reported as an AE and the associated laboratory result/vital sign will be considered as additional information. Wherever possible the reporting investigator uses the clinical, rather than the laboratory term (e.g., anemia versus low hemoglobin value). In the absence of clinical signs or symptoms, clinically relevant deteriorations in non-mandated parameters should be reported as AE(s).

Deterioration of a laboratory value, which is unequivocally due to disease progression, should not be reported as an AE/SAE.

Any new or aggravated clinically relevant abnormal medical finding at a physical examination as compared with the baseline assessment will be reported as an AE.

Disease progression

Disease progression can be considered as a worsening of a subject's condition attributable to the disease for which the investigational product is being studied. It may be an increase in the severity of the disease under study and/or increases in the symptoms of the disease. The development of new, or progression of disease, or death attributable to breast cancer should be considered as disease progression and not an AE. Events, which are unequivocally due to disease, should not be reported as an AE.

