6.4.4 Reporting of serious adverse events

Investigators and other site personnel must inform the FDA, via a MedWatch form, of any serious or unexpected adverse events that occur in accordance with the reporting obligations of 21 CFR 312.32, and will concurrently forward all such reports to AstraZeneca and Pfizer. A copy of the MedWatch report must be faxed to AstraZeneca and Pfizer at the time the event is reported to the FDA. It is the responsibility of the investigator to compile all necessary information and ensure that the FDA receives a report according to the FDA reporting requirement timelines and to ensure that these reports are also submitted to AstraZeneca and Pfizer at the same time.

When reporting to AstraZeneca and Pfizer, a cover page should accompany the MedWatch form indicating the following:

- Investigator Sponsored Study (ISS)
- The investigator IND number assigned by the FDA
- The investigator's name and address
- The trial name/title and AstraZeneca ISS reference number

Investigative site must also indicate, either in the SAE report or the cover page, the causality of events in relation to all study medications and if the SAE is related to disease progression, as determined by the principal investigator.

Send SAE report and accompanying cover page to AstraZeneca by email to AE Mailbox Clinical Trial (TCS) <[contact]> or by fax to [name] (US Fax number). Email is the preferred method. Send SAE report and accompanying cover page to Pfizer by email to AE Mailbox Clinical Trial (TCS) <XXX> or by fax to 1-XXXXXXX (US Fax number). Email is the preferred method.

Serious adverse events that do not require expedited reporting to the FDA need to be reported to AstraZeneca and Pfizer preferably using the MedDRA coding language for serious adverse events.

All SAEs have to be reported to AstraZeneca and Pfizer, whether or not considered causally related to the investigational product. All SAEs will be documented. The investigator is responsible for informing the IRB and/or the Regulatory Authority of the SAE as per local requirements.

All SAE's should be reported to AstraZeneca and Pfizer within 5 days.

Institutional Review Board

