11. EVALUATION AND CALCULATION OF VARIABLES

11.1 Calculation or derivation of efficacy variable(s)

The primary objectives of the study are descriptive assessments of ESR1 mutation detection in plasma. One of the secondary endpoints of the study is PFS. PFS is defined as the duration of time from time of randomization to time of progression or death, whichever occurs first. PFS for a subject without an event will be censored on the date of last tumor assessment. If an interval of 6 months passes without a tumor assessment, PFS will be censored at the time of the earlier tumor assessment, even if an event (progressive disease or death) is later observed. If a patient has not had an event, PFS will be censored at the date of the last adequate tumor evaluation. PFS will also be censored at the date of tumor evaluation when the next tumor evaluation (or death) is >6 months after the previous evaluation without an event. PFS will be assessed via local radiology assessment according to RECIST 1.1.

Although central review may occur as part of site calibration or an audit, the local assessment will be considered as the basis for the primary efficacy analysis. In the absence of measurable disease at baseline, the following criteria (per RECIST 1.1) will be used to assess disease progression among the patients with nonmeasurable lytic or mixed (lytic + blastic) bone lesions: 1) The appearance of one or more new lesions or 2) Unequivocal progression of existing non-measurable lesions.

Additional secondary endpoints include response rate, clinical benefit rate, (defined as CR+PR+ SD at any tumor assessment), clinical benefit rate at 6 months (CBR6), in the entire cohort, and the ESR1-mut cohorts. Response rate will be reported from best overall response according to RECIST 1.1 and as described in section 6.3. The response rate will then be compared amongst the tamoxifen plus palbociclib and fulvestrant plus palbociclib arms in the entire cohort and in the subgroup of ESR1-mt patients.

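### Section 6.4.3 uses two incompatible tests to exempt disease-related events from AE reporting, and the looser one lets possibly drug-related symptoms and deaths leave the safety comparison before causality is recorded

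*Combined protocol and SAP*

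**What the plan says.** **The exemption (6.4.3, Disease progression).** Progression is described as worsening attributable to the disease under study: "It may be an increase in the severity of the disease under study and/or increases in the symptoms of the disease". The rule then follows: "The development of new, or progression of disease, or death attributable to breast cancer should be considered as disease progression and not an AE". The closing sentence sets a different threshold: "Events, which are unequivocally due to disease, should not be reported as an AE".

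**SAE reporting (6.4.4, 6.4.5).** All SAEs go to the two companies whatever their relation to the drug. Sites must also state "if the SAE is related to disease progression, as determined by the principal investigator". Section 6.4.5 supplies a five-level causality scale for SAEs.

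**Efficacy (6.3, 6.3.4, 11.1).** "PFS will be assessed via local radiology assessment according to RECIST 1.1". A PFS event is progression or death, with no restriction by cause. "Patients with a global deterioration of health status requiring discontinuation of treatment without objective evidence of disease progression" are to be reported under a separate label, symptomatic deterioration, with an instruction to try to document objective progression afterwards. Table 2 does not class that label as progressive disease.

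**Use of the safety data (2.1, 11.2, 12.1).** "Safety and toxicity assessment" is the fourth primary objective. AE rates are compared between arms by a mid-P Fisher test, and AEs and SAEs are tabulated by treatment group.

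**The concern.** Exempting documented progression from AE reporting is a defensible choice. The difficulty is that the section gives sites two thresholds and no way to choose between them. Fatigue, dyspnea, bone pain or liver failure in metastatic breast cancer can come from the disease or the drug, and the protocol's own adverse-effect lists in 5.2.1 contain such terms. Under the looser test, the investigator settles the question before anything is recorded as an AE.

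The trial is open label (3.2). If the disease label is applied more readily in one arm than in the other, an AE difference can be created or hidden. The ambiguity also need not be neutral between arms: the tamoxifen list includes tumor pain and local disease flare (among effects below 1% or of undefined frequency), which could be read as increased symptoms of the disease. The fulvestrant list has no such item.

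**Working it through.** The plan gives no figure to reproduce. The check sets the sections side by side, with two small calculations.

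**1. The two tests applied to one event.** Take a symptom or death that is probably disease and possibly drug.
- 'Attributable' sentence of 6.4.3: not an AE.
- 'Unequivocally' sentence of 6.4.3: not exempt, so reportable.
- 6.4.1: deterioration of an existing condition is an AE whatever its cause, so reportable.
- Laboratory sentence of 6.4.3: also uses 'unequivocally', so the strict test already appears elsewhere in the section.

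**2. What an exempted event loses.** Under 6.4.2 an SAE is an AE that meets further criteria. An event that is not an AE therefore receives no CTCAE grade and no yes/no causality rating (6.4.3), no progression flag (6.4.4) and no causality category (6.4.5). Probable cause of death is listed in 6.4.3 only among the SAE variables. Follow-up collects disease status and survival (6.2; Table 4, note n). The plan names no other place where the reason for attributing a death to disease is recorded.

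**3. Do exempted deaths also leave PFS?** Inputs: 28-day cycles, assessment every 2 cycles (6.3), censoring when the next evaluation or death is more than 6 months after the last one (11.1).
- Assessment interval: 2 × 28 = 56 days.
- Window: 6 months ≈ 183 days; 183 / 56 = 3.3.
- Scans due 56, 112 and 168 days after the last one would all have to be missing before a death was censored.

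On treatment and on schedule, a death falls inside the window and is a PFS event. Censoring is plausible mainly off treatment, where CT is optional (Table 4). Even then the death enters the overall survival analysis (12.1).

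**4. Does symptomatic worsening leave both?**
- Non-measurable disease: 6.3 accepts clinical worsening from the non-measurable site as progression, so it is a PFS event. Section 11.1 lists only new lesions or unequivocal progression for non-measurable lytic or mixed bone lesions. The two do not match.
- Measurable disease without objective progression: symptomatic deterioration is not a PFS event, and it is exempt from AE reporting if attributed to disease. It stays out of both unless progression is documented later or the patient dies within the window.

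**5. Size per patient.** With 20 per arm (12.2), 1 / 20 = 5 percentage points. Section 11.2 counts the highest grade for each AE for each patient, so the shift applies to one AE term, and only if that patient has no other record of it.

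Purely as illustration, suppose k patients with the same AE term are all labelled disease in one arm and all labelled AE in the other. The two-sided mid-P is 0.5 × 2 × C(20,k)/C(40,k):

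| k | Difference | Mid-P |
|---|---|---|
| 2 | 10 points | 190/780 = 0.24 |
| 3 | 15 points | 1140/9880 = 0.12 |
| 4 | 20 points | 4845/91390 = 0.053 |

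Nothing in the documents supports a particular k or such complete opposite labelling.

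**The case against.** **The paragraph can be read as one rule.** It may be meant to describe progression first and then exempt only what is unequivocally disease. On that reading the flag in 6.4.4 makes sense: it marks SAEs related to progression but not unequivocally due to it. This is a fair account of what was probably intended. But the 'attributable' sentence is not only a description; it says in its own words that such events are not AEs. A site following it literally has little left to flag. The objection therefore supports keeping the strict test and deleting the other.

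**A reader might infer that PFS counts only RECIST progression, so that exempted deaths vanish from both analyses.** The documents do not support that. Death from any cause is a PFS event, the gap rule removes it only in unusual circumstances, and overall survival is analysed as well.

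**A reader might also infer that relabelling would leave no trace.** That goes too far. Reasons for stopping treatment must be documented (5.6), symptomatic deterioration has its own label (6.3.4), symptoms are assessed every 4 weeks (Table 4), and 6.4.3 requires new or worsened clinically relevant examination findings to be reported as AEs. What is missing is grade, causality and a progression flag for the exempted event, and a stated by-arm tabulation.

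**This is a 40-patient pilot with mainly descriptive aims.** True, and it limits the consequences. Safety is nonetheless a listed primary objective with a planned between-arm comparison.

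**Conclusion.** The point holds as an inconsistency in the AE exemption and should be corrected. Section 6.4.3 has two thresholds that give opposite answers for events that are probably disease but possibly drug. Under the looser one, unblinded investigators can remove such symptoms and deaths from the safety comparison before causality is assessed.

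The reach is limited. Deaths generally remain in PFS and overall survival. Apart from the 6-month gap rule, the event that can be absent from both the AE table and PFS is symptomatic deterioration in measurable disease with no later documented progression and no death within the window. This assumes that 6.3 governs non-measurable disease; if 11.1 governs, the gap could extend to patients with non-measurable bone disease.

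The size is at most 5 percentage points per relabelled patient per AE term. The number of such patients, and whether labelling would differ by arm, are unknown; the table above is illustration, not estimate. No sample-size, power or alpha figure changes.

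**What to change.** 1. In 6.4.3, keep one test: exempt only events unequivocally due to progression that is documented under 6.3 and 11.1. Drop 'attributable' as the test for exempting symptoms and deaths.
2. Record symptomatic deterioration that does not meet this test as an AE with grade and causality.
3. Record deaths on treatment and up to the final toxicity assessment (Table 4, note m, at least 30 days after the last dose) as SAEs carrying the progression flag that 6.4.4 already requires. The limit is needed because 6.4.6 gives no end to AE collection and 6.4.2 extends SAEs into follow-up, which runs until death; without it, most deaths in this metastatic cohort could become SAEs.
4. In 11.2 and 12.1, tabulate AEs and SAEs by arm with and without flagged events.
5. Reconcile 6.3 with 11.1 on whether clinical worsening counts as progression in non-measurable disease.

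Cost: protocol wording, one extra tabulation and a few more AE/SAE lines for 40 patients, some of which will turn out to be disease. The flag already exists.

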6.4.4 Reporting of serious adverse events

Investigators and other site personnel must inform the FDA, via a MedWatch form, of any serious or unexpected adverse events that occur in accordance with the reporting obligations of 21 CFR 312.32, and will concurrently forward all such reports to AstraZeneca and Pfizer. A copy of the MedWatch report must be faxed to AstraZeneca and Pfizer at the time the event is reported to the FDA. It is the responsibility of the investigator to compile all necessary information and ensure that the FDA receives a report according to the FDA reporting requirement timelines and to ensure that these reports are also submitted to AstraZeneca and Pfizer at the same time.

When reporting to AstraZeneca and Pfizer, a cover page should accompany the MedWatch form indicating the following:

- Investigator Sponsored Study (ISS)
- The investigator IND number assigned by the FDA
- The investigator's name and address
- The trial name/title and AstraZeneca ISS reference number

Investigative site must also indicate, either in the SAE report or the cover page, the causality of events in relation to all study medications and if the SAE is related to disease progression, as determined by the principal investigator.

Send SAE report and accompanying cover page to AstraZeneca by email to AE Mailbox Clinical Trial (TCS) <[contact]> or by fax to [name] (US Fax number). Email is the preferred method. Send SAE report and accompanying cover page to Pfizer by email to AE Mailbox Clinical Trial (TCS) <XXX> or by fax to 1-XXXXXXX (US Fax number). Email is the preferred method.

Serious adverse events that do not require expedited reporting to the FDA need to be reported to AstraZeneca and Pfizer preferably using the MedDRA coding language for serious adverse events.

All SAEs have to be reported to AstraZeneca and Pfizer, whether or not considered causally related to the investigational product. All SAEs will be documented. The investigator is responsible for informing the IRB and/or the Regulatory Authority of the SAE as per local requirements.

All SAE's should be reported to AstraZeneca and Pfizer within 5 days.

Institutional Review Board

All adverse events (AEs) and serious adverse events (SAEs) will be reported to the IRB per current institutional standards. If an adverse event requires modification of the informed consent, these modifications will be provided to the IRB with the report of the adverse event. If an adverse event requires modification to the study protocol, these modifications will be provided to the IRB as soon as is possible.

6.4.5 Causality of Adverse Event by Study Compound

The causality of SAEs (their relationship to all study treatment/procedures) will be assessed by the investigator(s) and communicated to AstraZeneca.

- Definitely: An adverse event which has a timely relationship to the administration of the investigational drug/agent, follows a known pattern of response, for which no alternative cause is present.
- Probably: An adverse event, which has a timely relationship to the administration of the investigational drug/agent, follows a known pattern of response, but for which a potential alternative cause may be present.
- Possibly: An adverse event, which has a timely relationship to the administration of the investigational drug/agent, follows no known pattern of response, but a potential alternative cause does not exist.
- Unlikely: An adverse event which does not have a timely relationship to the administration of the investigational drug/agent, follows no known pattern of response, does not reappear or worsen after re-administration of the investigational drug/agent (if applicable), and for which there is evidence that it is related to a cause other than the investigational drug/agent.
- Unrelated: An adverse event, for which there is evidence that it is definitely related to a cause other than the investigational drug/agent. In general, there is no timely relationship to the administration of the investigational drug/agent, or if there is a timely relationship, the event does not follow a known pattern of response, and there is an alternative cause.

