6.4.3 Recording of Adverse Events

General: All adverse events will be captured on the appropriate study-specific case report forms (CRFs).

Serious Adverse Events: All serious adverse events, regardless of causality to study drug, will be reported to the Principal Investigator and/or the Study Coordinator at each institution, and also to the Coordinating Center.

All serious adverse events must be reported to the Coordinating Center within 1 business day after the investigator becomes aware of the event. Events should be reported using a MedWatch form (3500) as available on the FDA website (<http://www.fda.gov/Safety/MedWatch>). Follow-up information must also be reported within 1 business day of receipt of the information by the investigator.

The Coordinating Center will disseminate information regarding serious adverse events to the participating sites within 5 days of review of the information by the Protocol Chair (or her designee in the event of extended absence) only in the case that the event(s) is believed to be related (i.e., possibly, probably, or definitely) to the study medication.

The following variables will be collected for each AE:

- AE (verbatim)
- The date when the AE started and stopped
- CTCAE grade
- Whether the AE is serious or not
- Investigator causality rating against the Investigational Product (yes or no)
- Action taken with regard to investigational product
- AE caused subject's withdrawal from study (yes or no)
- Outcome.

In addition, the following variables will be collected for SAEs:

- Date AE met criteria for serious AE
- Date Investigator became aware of serious AE
- AE is serious due to
- Date of hospitalization
- Date of discharge
- Probable cause of death
- Date of death
- Autopsy performed
- Causality assessment in relation to Study procedure(s)
- Causality assessment in relation to Other medication
- Causality assessment in relation to Additional Study Drug
- Description of AE.

It is important to distinguish between serious and severe AEs. Severity is a measure of intensity whereas seriousness is defined. An AE of severe intensity need not necessarily be considered serious. For example, nausea that persists for several hours may be considered severe nausea, but not a SAE. On the other hand, a stroke that results in only a limited degree of disability may be considered a mild stroke but would be a SAE.

Adverse Events based on signs and symptoms

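### The causality scale has no related class for a timely SAE of unknown pattern with a potential alternative cause, so such an SAE can miss the alert to participating sites

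*Combined protocol and SAP*

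**What the plan says.** Section 6.4.5 (Causality of Adverse Event by Study Compound) has the investigator assess the causality of SAEs and defines five classes. They are built on three features: timing relative to the drug, whether the event fits a known pattern of response, and whether something else could explain it.

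- *Definitely*: timely, known pattern, no alternative cause.
- *Probably*: a timely event that "follows a known pattern of response, but for which a potential alternative cause may be present".
- *Possibly*: a timely event that "follows no known pattern of response, but a potential alternative cause does not exist".
- *Unlikely*: for an event with no timely link to dosing, with further conditions.
- *Unrelated*: opens with "An adverse event, for which there is evidence that it is definitely related to a cause other than the investigational drug/agent". A second sentence, introduced as a generality, describes events that are not timely, "or if there is a timely relationship, the event does not follow a known pattern of response, and there is an alternative cause".

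Section 6.4.3 (Recording of Adverse Events) makes the classes operative. After review by the Protocol Chair or designee, the Coordinating Center passes SAE information to participating sites "only in the case that the event(s) is believed to be related", and names *possibly*, *probably* and *definitely* as what related means.

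For each adverse event the same section lists the item "Investigator causality rating against the Investigational Product (yes or no". For SAEs it adds further causality items, such as "Causality assessment in relation to Additional Study Drug", with no answer scale stated.

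**The concern.** The three related classes treat an alternative cause unevenly. For a familiar event, a possible competing explanation lowers the rating one step, from *Definitely* to *Probably*, and the event stays related. For an unfamiliar event, the same competing explanation removes it from the related classes altogether, because *Possibly* is closed to it.

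A previously unrecognised toxicity is by definition an event without a known pattern. If it also has a plausible competing cause, the written rule gives other sites no notice of it.

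Safety and toxicity is a listed primary objective (section 2.1). The Background (section 1.1) says that no trial was then examining these two palbociclib combinations against each other after earlier CDK4/6 exposure. Patients have metastatic disease (section 4.1) and may have had up to three endocrine lines and one chemotherapy line for it (section 4.2), so competing explanations are plausible.

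**Working it through.** The plan gives no figure here, so the check is an enumeration of the 6.4.5 definitions followed by the 6.4.3 alert rule. Two yes/no features remain once an event is timely, which gives 2 × 2 = 4 combinations.

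| Timely event | Potential alternative cause | Class under 6.4.5 | Site alert under 6.4.3 |
|---|---|---|---|
| Known pattern | No | *Definitely* | Yes |
| Known pattern | Yes | *Probably* | Yes |
| No known pattern | No | *Possibly* | Yes |
| No known pattern | Yes | No related class | No |

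The fourth row, class by class:

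1. *Definitely* and *Probably* both need a known pattern. The event fails both.
2. *Possibly* needs the absence of any potential alternative cause. The event fails.
3. *Unlikely* is for an event without a timely relationship. The event fails.
4. *Unrelated*, second sentence: this is the only text in the scale that describes a timely event of no known pattern with an alternative cause. *Unrelated*, first sentence: requires evidence that the other cause is definite. If the other cause is only potential, that condition is not met.

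So if the other cause is definite, *Unrelated* fits and no alert is the intended result. If it is only potential, no class strictly fits, and the nearest description is in *Unrelated*. In both cases the event is outside the three classes that 6.4.3 names, and the literal rule sends no alert. The defect is confined to the second case.

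Applying the wording proposed below to the fourth row: a merely potential other cause gives *Possibly* and an alert; evidence of a definite other cause gives *Unrelated* and no alert. The other three rows do not change.

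**The case against.** The best case on the other side is that little depends on the gap. All SAEs go to the institution's principal investigator and/or study coordinator and to the Coordinating Center whatever their causality, within 1 business day (6.4.3). All go to AstraZeneca and Pfizer on the same basis, and adverse events and SAEs go to the IRB (6.4.4). The Principal Investigator reviews SAEs and the data from all sites (9.2). Only onward notice to the other sites is exposed, in a study of 40 evaluable patients at up to 4 sites (3.1). This stands, and it is why the point is minor. It does not close the gap, because 6.4.3 is where the plan describes how SAE information reaches the participating sites, and its test is relatedness.

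It can also be said that the Protocol Chair reviews the event first and could call it possibly related anyway. That may happen in practice, but the Chair would then be setting aside the only definition of the term in the protocol.

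Four stronger readings are tempting, and the documents do not support them:

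- *Any alternative cause makes an unfamiliar event Unrelated.* The first sentence of that class requires a definite other cause. A merely potential one falls between classes.
- *The yes/no field causes the filtering.* The alert rule does not use that field. The field is in the list for every adverse event; SAEs carry further causality items, and 6.4.4 requires causality for all study medications on the SAE report or cover page.
- *New toxicities in general are filtered out.* A timely, unfamiliar SAE with no alternative cause is *Possibly* and is alerted.
- *In metastatic cancer the disease is nearly always a potential alternative cause.* The documents give no such frequency. They also treat disease separately: events unequivocally due to it are not reported as adverse events (6.4.3), and relation to progression is stated for each SAE (6.4.4).

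**Conclusion.** The stated rule is wrong as written, and the severity is minor. One of the four timely combinations has no related class, and read with 6.4.3 it triggers no site alert. That is a count of rule combinations and not a share of events; the documents give no basis for estimating how many SAEs would fall there.

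The conclusion rests on two assumptions: that the three labels in 6.4.3 carry the meanings defined in 6.4.5, and that the definitions are applied literally.

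A reader might infer that safety analysis or central oversight is compromised. The documents do not support that. The adverse event rates in 11.2 and the tables in 12.1 state no causality restriction, and the central reporting routes do not depend on causality.

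That the yes/no item is not mapped to the five classes is a separate documentation point and not a defect in the alert rule.

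**What to change.** In 6.4.5, reword *Possibly* along these lines: timely relationship; no known pattern of response; a potential alternative cause may or may not be present. Keep the pattern condition. Opening the class to events with a known pattern would make it overlap with *Definitely* and *Probably*.

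In the second sentence of *Unrelated*, limit the timely case to events with evidence of a definite other cause, so that it agrees with the first sentence.

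Section 6.4.3 then needs no change to its alert rule. At most, add a line saying which of the five classes count as yes in the per-event causality item. Collecting all five levels for every adverse event is not needed to close the gap.

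The cost is the rewording of two definitions and a few more SAE notices to sites. No analysis or sample size changes.
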